2.2 Experimental Subjects

The patients were randomly divided into 3 groups according to the random number table method:

Remimazolam group (Group R): After intubation, remimazolam was maintained at a pump rate of 1-2 mg/kg/h until 10 minutes before the end of the operation.

Propofol group (Group P): After intubation, propofol was maintained at a pump rate of 4-10mg/kg/h until 10 minutes before the end of the operation.

Remimazolam combined with propofol group (Group C): After intubation, remimazolam at a dose of 0.3-1mg/kg/h and propofol at a dose of 3-6 mg/kg/h were maintained until 10 minutes before the end of the operation.

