3.3 Cardiovascular responses of patients at all times during the perioperative period

Record the heart rate, mean arterial pressure and pulse oxygen saturation of the patient at the time of entering the room (TO), before OLV (T1), 30 minutes after OLV (T2), 60 minutes after OLV (T3), before extubation (T4), and 5 minutes after extubation (T5).

3.4 Intraoperative blood gas analysis:

All patients underwent arterial blood gas analysis and central venous blood gas analysis before OLV (T1), 30 minutes after OLV (T2), and 60 minutes after OLV (T3). Record the Pplat, VT, PEEP, OI, PaO₂, PAO₂, PcvO₂, SaO₂, ScvO₂, (A-a)DO₂, RI at these three moments, and calculate Qs/Qt and Cdyn.

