Data analysis was conducted using SPSS 27.0 statistical software. Normally distributed measurement data were expressed as mean \pm standard deviation, and the comparison between groups was performed using the independent sample t-test; non-normally distributed measurement data were expressed as median and interquartile range [M(IQR)], and the comparison between groups was conducted using the Wilcoxon rank sum test. Count data were expressed as cases (%), and the comparison between groups was performed using the χ^2 test or Fisher's exact probability method. A P value < 0.05 was considered statistically significant.

The main endpoint of this study is the oxygenation index measured at 60 minutes (T3) during OLV. According to the literature, the oxygenation index of patients when they are breathing pure oxygen in both lungs and are in a state of good oxygenation is generally

between 350 and 400 mmHg. After switching to OLV, the oxygenation index drops to 150 to 200 mmHg. Therefore, any change in the oxygenation index within 50 mmHg during OLV is not clinically significant. Thus, 50 mmHg is set as the cutoff value for the disadvantage. That is, in this study, if the oxygenation index of the study group is lower than that of the control group at T4, but the difference in oxygenation indices between the two groups is within 50, then the ventilation strategy of the study group is not inferior to that of the control group in improving intraoperative oxygenation. Taking the type I error probability $\alpha = 0.025$ and the type II error probability $\beta = 0.20$, power value 0.80; using SPSS 27.0 software, the sample size for each group was calculated to be 38. Considering a 20% dropout rate and withdrawal rate, the final required sample size for each group was 50.

V. Management of Experimental Data of Subjects

1. Strictly follow the provisions of Article 1034 of the Civil Code: The personal information of natural persons is protected by law; Article 1038 stipulates: Information processors shall not disclose or tamper with the personal information they have collected and stored. Without the consent of the natural person, they shall not illegally provide the personal information to others. Protect the privacy of the subjects and prevent it from being leaked.

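### The non-inferiority rule compares the observed difference with 50 mmHg and uses no confidence limit, so an arm truly worse by the full margin passes about half the time

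*Protocol*

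**What the plan says.** All of the relevant analysis text is in the protocol, section IV (Statistical Analysis), unless noted.

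- **Endpoint:** "The main endpoint of this study is the oxygenation index measured at 60 minutes (T3) during OLV".
- **Margin:** "Thus, 50 mmHg is set as the cutoff value for the disadvantage".
- **Decision rule:** the case considered is "if the oxygenation index of the study group is lower than that of the control group at T4". Non-inferiority is declared in that case on one further requirement: "but the difference in oxygenation indices between the two groups is within 50".
- **Tests for continuous data:** for normal data, "the comparison between groups was performed using the independent sample t-test"; for non-normal data, "the comparison between groups was conducted using the Wilcoxon rank sum test". Significance is P below 0.05.
- **Sample size:** alpha 0.025, power 0.80, 38 per group, raised to 50 for 20% dropout. No SD and no assumed true difference are given. Alpha 0.025 appears only here.
- **Blood gases (section 3.4):** taken "before OLV (T1), 30 minutes after OLV (T2), and 60 minutes after OLV (T3". Section 3.3 defines T4 as the time before extubation.
- **Arms (section 2.2):** "The patients were randomly divided into 3 groups according to the random number table method". These are R (remimazolam), P (propofol) and C (both). None is called the control.

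**The concern.** A non-inferiority claim needs evidence that the true deficit is smaller than the margin. That means a confidence limit clear of the margin, or a test whose null hypothesis is a deficit of 50 mmHg or more. The protocol writes a complete if/then criterion with neither, so the natural reading is a rule on the observed difference, with no allowance for sampling error. The listed tests do not fill the gap. As ordinary comparisons they test zero difference: a significant result does not place the deficit inside the margin, and a non-significant one does not show that it is small. The P < 0.05 threshold is not the problem, since a two-sided 0.05 level matches a one-sided 0.025 limit. The problem is the null hypothesis.

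The sentence also cannot be carried out as written. It needs an oxygenation index at T4, which the blood gas schedule does not provide, and it describes two groups in a three-arm trial. The primary conclusion would then depend on choices of rule, time point and control made after the data are seen.

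**Working it through.** **Inputs.** From the protocol: margin 50 mmHg, alpha 0.025 (taken as one-sided), power 0.80, 38 per group, 50 enrolled, 20% dropout. Evaluable per group: 50 × 0.8 = 40. Assumption, because no SD is given: SD 50 to 100 mmHg.

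**1. The plan's own figure.** Without an SD, 38 cannot be checked independently, but it can be solved for the SD it implies:
- True difference 0: SD = 50 × √(38/2) / (1.960 + 0.842) = 77.8 (76.8 with the t distribution).
- True deficit 10: SD = 40 × √19 / 2.802 = 62.2 (61.4 with t).

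So 38 per group is consistent with a one-sided 0.025 test against the margin at an SD of about 77. The written rule is not that test.

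**2. Rule as written, true deficit equal to the margin.** Let d be study minus control and δ its true value, with SE = SD × √(2/n).

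P(pass) = P(observed d > -50) = Φ((δ + 50)/SE)

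At δ = -50 this is Φ(0) = 0.50 for every SD and n. If the observed deficit must also lie between 0 and 50, it is 0.485 to 0.500 over the SDs and group sizes tried. A rule based on the two-sided 95% CI gives 0.025.

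**3. True deficits beyond the margin, and the CI cut-off (n = 40).** The cut-off is the observed d above which the CI rule passes: -50 + 1.991 × SE.

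| SD | SE | As written, δ = -60 | As written, δ = -70 | CI rule, δ = -60 | CI cut-off for d |
|---|---|---|---|---|---|
| 50 | 11.2 | 0.186 | 0.037 | 0.0022 | -27.7 |
| 62 | 13.9 | 0.235 | 0.075 | 0.0038 | -22.4 |
| 77 | 17.2 | 0.281 | 0.123 | 0.0056 | -15.7 |
| 100 | 22.4 | 0.327 | 0.186 | 0.0082 | -5.5 |

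Example: SD 77, δ = -60 gives Φ(-10/17.2) = 0.281.

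**4. Two arms against one shared control of equal size, both at δ = -50.** The two estimated differences have correlation 0.5.
- P(both fail) = 1/4 + arcsin(0.5)/(2π) = 1/3, so P(at least one passes) = 2/3.
- With an unadjusted CI rule the corresponding figure is 0.045.

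**5. If non-significance on the listed test were taken as non-inferiority.** At a true deficit of 50 and 38 per group, the normal approximation gives a pass rate of about 1% at SD 50, 20% at SD 77.8 and 41% at SD 100. This does not hold 0.025 either.

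**6. Power of the CI rule (38 per group, SD 77).**
- True difference 0: 0.798 at one-sided 0.025, and 0.706 at 0.0125.
- True deficit 10: about 0.61.
- Both of two comparisons passing, true difference 0: about 0.68 (0.71 at 40 per group).

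**The case against.** The sentence can be read as explaining the margin rather than fixing a decision rule. It follows directly on the choice of 50 mmHg and leads into the sample-size inputs. A rule on the observed difference would leave alpha 0.025 with no role, and 38 per group fits a margin test at a plausible SD. The t-test is named generically for all normal data, and the t-based interval is exactly what a correct analysis would use. A SAP that is not shown may specify the limit. T4 may be a labelling slip, and the 67% assumes two comparisons with a shared control, which the protocol does not state.

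Part of this stands. A one-sided margin test was probably intended, the 50% belongs to the literal reading, and the 67% belongs to a two-comparison design. The main point remains. The protocol goes beyond defining a margin: it says what result leads to the conclusion of non-inferiority, and a SAP that adds a confidence limit would have to replace that criterion. On the margin-only reading, the tests are still stated as ordinary comparisons with nothing set against 50 mmHg. T4 contradicts the protocol's own endpoint and sampling times, whatever its origin.

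**Conclusion.** The concern holds and should be fixed before any outcome is analysed. As written, the criterion for the primary conclusion does not deliver the 0.025 error rate used for sizing. On the literal reading the rate at the margin is 0.50, which is 20 times as high (0.50/0.025), and this figure needs no assumption about SD or n beyond a symmetric estimate. A regimen worse by 60 mmHg would still pass in 19% to 33% of trials. That range rests on an assumed SD of 50 to 100 mmHg and 40 evaluable per group. The two-arm figure of 67% applies only if both other arms are compared with one control and both lie at the margin. The time point and the control must be settled in the same correction, because the rule cannot be applied without them.

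**What to change.** Replace the decision sentence with:

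> Non-inferiority is shown if the lower limit of the two-sided 95% CI (one-sided alpha 0.025) for the difference in mean oxygenation index at T3 (study group minus control) is above -50 mmHg.

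Then:
- Name the control. Group P is the only arm without remimazolam, but the protocol does not call it the control, so the sponsor must confirm.
- State whether R, C or both are compared with it. If both, either fix the order and test the second only if the first passes, each at one-sided 0.025, or split alpha and resize.
- Optionally, allow a superiority test at the same alpha within a comparison once non-inferiority is shown.
- State the planning SD and the assumed true difference.

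**Cost.** This is a wording change and a stricter hurdle than the literal text. For a single comparison, or the first step of a fixed order, 38 per group is enough if the true difference is 0 and the SD is about 77 or less. If a true deficit of 10 is to be allowed for, the SD must be about 62 or less. At SD 77 and true difference 0, splitting alpha to 0.0125 lowers power per comparison from about 80% to 71%, and power to pass both steps of a fixed order is about 68%. If both conclusions are wanted at 80% power under those assumptions, more patients are needed.

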2.5 Anesthesia induction and maintenance

After the pre-anesthesia preparations were completed, anesthesia induction began. After 3 minutes of mask inhalation of pure oxygen, the three groups were successively given fentanyl 3-5 μ g/kg, etomidate 0.4 mg/kg, and cisatracurium 0.15 mg/kg. After mask controlled oxygen inhalation for 5 minutes, after the relaxation of the mandibular muscles and anesthesia induction, a double-lumen endobronchial tube (DLT) was inserted to ensure good alignment. The anesthesia machine was adjusted to volume-controlled ventilation, and the respiratory parameters were adjusted: the tidal volume was regulated by 6-8 ml/kg and the respiratory rate was maintained to keep the end-expiratory CO₂ partial pressure at 35-45

mmHg. After the anesthesia stabilizes, a retrograde puncture and catheterization of the internal jugular vein is performed. The puncture point beside the thyroid cartilage is determined. After disinfection and laying a towel, the puncture is performed and a catheter is placed. The catheter is fixed with sutures and fluid replacement is carried out during the operation. Anesthesia maintenance: Total intravenous anesthesia was used during the operation. Intravenous anesthetics were continuously pumped according to the groups. Group R: Remimazolam was maintained at a pumping rate of 1-2mg/kg/h. Group P: Propofol was maintained at a pump speed of 4-10mg/kg/h. Group C: Maintained with remimazolam at a dose of 0.3-1mg/kg/h and propofol at a dose of 3-6 mg/kg/h. All three groups were combined with remifentanil at 6-12 μ g/kg/h, and the drug pumping speed was adjusted to maintain the BIS value at 40-60. Thirty minutes before the end of the operation, 0.15 mg/kg dezocine was administered. The infusion of remimazolam and propofol was stopped 10 minutes before the operation, and remifentanil was stopped 5 minutes before the operation.

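### Three arms are randomised, but the non-inferiority rule compares two unnamed groups, is set at T4 instead of T3, and uses no confidence limit

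*Protocol*

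**What the plan says.** **Design.** Protocol section 2.2: "The patients were randomly divided into 3 groups according to the random number table method". The arms are R (remimazolam), P (propofol) and a second remimazolam-containing arm, "Remimazolam combined with propofol group (Group C"). Section 2.5 repeats the same three arms: "All three groups were combined with remifentanil".

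**Endpoint.** Section IV: "The main endpoint of this study is the oxygenation index measured at 60 minutes (T3) during OLV". Section 3.4 schedules blood gases "before OLV (T1), 30 minutes after OLV (T2), and 60 minutes after OLV (T3"), and lists the oxygenation index among the values recorded at those three times. Section 3.3 defines T4 as before extubation.

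**Decision rule.** Section IV sets a margin of 50 mmHg and applies it "if the oxygenation index of the study group is lower than that of the control group at T4". If "the difference in oxygenation indices between the two groups is within 50, then the ventilation strategy of the study group is not inferior" to the control.

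**Tests and size.** For normally distributed data, "the comparison between groups was performed using the independent sample t-test"; otherwise a Wilcoxon rank sum test is used. Section IV gives one type I error (0.025, sidedness not stated), one power (0.80) and one sample size: 38 in each group, raised to 50 for 20% loss.

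**The concern.** The rule that decides the primary conclusion does not fit the design in three respects.

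1. **Which comparison.** The rule has two groups and the trial has three. P is the natural control, but then R and C are both candidates for the single study group. If R met the margin and C did not, one reader could report non-inferiority and another could report failure, each citing the same sentence. The sentence also judges a ventilation strategy, whereas the arms differ in maintenance drug, so it does not help to match labels to arms.
2. **Which time.** The margin is applied at T4, when no blood gas is scheduled. Taken literally, the rule cannot be evaluated on the planned data.
3. **Which quantity.** The rule compares the difference itself with 50, rather than a confidence limit.

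What is at stake is that the deciding comparison could be settled after the results are known. Depending on the choice, the stated error rate or power might no longer describe the trial.

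**Working it through.** **Inputs from section IV.** Margin 50 mmHg; type I error 0.025; power 0.80; 38 evaluable per group; 50 enrolled per group; 20% loss. The text gives no standard deviation (SD) and no expected difference.

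**The plan's own figure.** For one non-inferiority comparison with true difference 0:

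n per group = 2 × [SD × (z for alpha + z for power) / margin]²

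Without an SD, 38 cannot be reproduced directly. Solving for the SD at one-sided 0.025:

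SD = 50 × √(38/2) / (1.960 + 0.842) = 50 × 4.359 / 2.802 ≈ 77.8 mmHg

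Allowing for rounding up, SDs from 76.8 to 77.7 return exactly 38. If 0.025 is two-sided, the range is 69.8 to 70.6. So 38 is what a single two-group comparison gives under an SD of this size. For the loss allowance, 38/0.8 = 47.5, hence 48; the stated 50 covers this. With 20% loss, 50 × 0.8 = 40 remain evaluable.

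**What each success rule would imply.** Assumptions: P is a shared control, the arms are equal in size, and each comparison has 80% power at 38 evaluable. Two estimates that share a control of equal size have correlation (SD²/n) / (2 × SD²/n) = 0.5, so I use a bivariate normal with that correlation. Given the 80% assumption, the results below do not depend on the SD.

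*One named comparison.* Error is 2.5% and power 80%, as stated.

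*Either regimen may succeed, with both truly at -50 mmHg.* P(at least one false claim) = 2 × (error per comparison) − P(both):
- 0.025 one-sided: 2 × 0.025 − 0.0046 = 0.0454, about 4.5%
- 0.025 two-sided, so 0.0125 on the relevant side: 2 × 0.0125 − 0.0018 = 0.0232, about 2.3%

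*Both must succeed, with equal true differences.* Error is at most 2.5%. The standardised mean is 2.802 × √(n/38), tested against 1.960:

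| Evaluable per group | Power, one comparison | Power, both |
|---|---|---|
| 38 | 0.800 | 0.687 |
| 40 (50 less 20%) | 0.820 | 0.715 |
| 50 (no loss) | 0.895 | 0.825 |

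**Difference against confidence limit.** If a regimen's true difference is exactly -50 mmHg, its estimate is distributed symmetrically about -50. It therefore falls inside the margin with probability 0.5. Read literally, the rule would pass such a regimen half the time, which is incompatible with the stated 0.025.

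**Time point.** T3 is 60 minutes of one-lung ventilation (sections 3.3, 3.4 and IV). T4 is before extubation (3.3). Blood gases are at T1, T2 and T3 (3.4). The rule's T4 agrees with neither the endpoint nor the schedule.

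**The case against.** The strongest reply is that the rule can be applied twice, to R and to C against P, as two separate claims at 0.025 each. The protocol sets no trial-wide error level, and whether separate claims about distinct regimens need adjustment is debated. The sample size is given for each group, which suits three arms: sizing one pairwise comparison and applying the result to every arm is common practice. Two-sample tests are valid for pairwise contrasts. Some protocol text is not available and might name the control, and testing order is commonly left to a statistical analysis plan, which is not shown. T4 may be a labelling slip; 24 hours after surgery is itself T7 in the outcome summary before section III and T6 in section 3.5. The stated 0.025 also suggests that a formal test is intended, rather than a bare comparison of the difference with 50.

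Much of this stands. A reader might infer that the error rate is inflated, that the trial is underpowered, that 38 per group is wrong for three arms, or that the t-test is inadmissible. The documents support none of these. The 4.5% needs 0.025 to be one-sided per comparison and also meant for the whole trial, with both regimens exactly at the margin. The 69% answers a rule requiring both regimens to succeed, which the protocol never states.

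The reply does not remove the mismatch in the text. The protocol does state a decision rule, and as written that rule refers to two groups in a three-arm trial and to a time with no blood gas. Naming P as control elsewhere would still leave R and C competing for one label. The T4 problem is separate from the number of arms and adds no weight to it, but it sits in the same sentence and needs correcting too.

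**Conclusion.** The point holds in a limited form. The non-inferiority rule in section IV does not identify which of the available comparisons decides the primary conclusion, is set at a time that conflicts with the main endpoint and the blood gas schedule, and is expressed on the difference instead of a confidence limit. The sample size is compatible with one pairwise comparison applied to all arms; 0.025 and 80% describe one comparison only.

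Whether any statistical harm follows depends on the intended rule. With one named comparison there is none. The other outcomes are alternatives that cannot both apply: about 4.5% (or 2.3%) for at least one false claim if either regimen may succeed, or joint power of about 69% at 38, 71% at 40 and 82% at 50 if both must. They rest on a shared control, equal arms and 80% power per comparison at 38 evaluable, and should be read as illustrations. The conflict in wording is certain; the failure to tie labels to arms is established only for the text available.

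**What to change.** In section IV:

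1. Name the control arm and the primary comparison, and state that 0.025 is one-sided.
2. If both R and C are to be claimed under a trial-wide 0.025, state the rule in advance. One reasonable option is a fixed sequence of the two comparisons with control, each at one-sided 0.025, in an order that the sponsor sets before any comparative data are seen.
3. Declare non-inferiority when the lower limit of the two-sided 95% confidence interval for regimen minus control, in oxygenation index at 60 minutes of one-lung ventilation, is above -50 mmHg. Reconcile T4 in the rule with T3 in the endpoint.
4. State 80% as the power for one comparison. If both claims are sought, give the joint figure as well (about 69% at 38 evaluable, 71% at 40).

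The cost is wording only, with no added patients. The drawback of a fixed sequence is that the second regimen cannot be formally claimed if the first fails.
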